Abbreviations: BP = blood pressure; C-SSRS = Columbia-suicide severity rating scale; CT = computed tomography; ECG = electrocardiogram; EQ-5D-5L = EuroQol - 5 Dimension - 5 Level; HbA1c = glycated hemoglobin; hsCRP = high-sensitivity C-reactive protein; IWQOL-Lite-CT = Impact of Weight on Quality of Life-Lite-Clinical trials version; MRI = magnetic resonance imaging; MRI-PDFF = magnetic resonance imaging - proton density fat fraction; NAFLD = non-alcoholic fatty liver disease; NASH = nonalcoholic steatohepatitis; OGTT = oral glucose tolerance test; PHQ-9 = Patient Health Questionnaire-9; PR = pulse rate; SF-36v2 = Short-Form 36-item Health Survey Version 2; TNFα = tumor necrosis factor-α; VAS = visual analog scale.

Protocol I8F-JE-GPHZ(b)

Table 3. Study Period III- Early Discontinuation and Follow-Up Period

Activity	Early Discontin	nuation and Follow-U	Comment			
Visit Number	99	ED	801	At ED visit, participants who are unable or unwilling to continue the study treatment for any reason will perform an ED visit. If the participant is discontinuing during an unscheduled visit or a scheduled visit, that visit should be performed as the ED visit. At Visit 801, for participants who discontinue or complete the study within 72 weeks, Visit 801 (safety follow-up visit) should be performed 4 weeks after the last visit during the 72-week treatment period.		
Weeks of treatment	72		4 weeks post end of treatment period			
Allowable duration (days)	±7		±7	The visit date after randomization visit is determined in relation to the date of the randomization visit (± the allowed visit window).		
Fasting visit	X	X	X	If the participant is not fasting, the participant should be called in for a new visit within the visit window.		
Adverse events and product complaints	X	X	X			
Hypoglycemic events	X	X	X			
Concomitant medications	X	X	X			
Lifestyle management counseling		X		Counselling on diet and exercise, to be performed by a dietician or equivalent qualified delegate, will include calculation of individualized energy requirement and methods to change dietary composition and amount of physical activity. The lifestyle management counseling may be delivered on a separate day from the rest of that visit's study procedures but must occur within the visit window.		
Review diet and exercise goals		X				
Participant returns study drugs and injection supplies		X				

Activity	Early Discontin	uation and Follow-U	Comment			

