Weight	X	Х	X	At Visit 99, participants wanting to discontinue the study before Week 72 will be asked to return for Visit 99 at 72 weeks ±7 days after randomization primarily for body weight measurement and assessment of adverse events. If the participant is unwilling to attend Visit 99, it should be documented in the participant medical record that the participant has refused to attend.

Activity	Early Discontinuation and Follow-Up Period		Comment	
Visit Number	99	ED	801	At ED visit, participants who are unable or unwilling to continue the study treatment for any reason will perform an ED visit. If the participant is discontinuing during an unscheduled visit or a scheduled visit, that visit should be performed as the ED visit. At Visit 801, for participants who discontinue or complete the study within 72 weeks, Visit 801 (safety follow-up visit) should be performed 4 weeks after the last visit during the 72-week treatment period.
Weeks of treatment	72		4 weeks post end of treatment period	
Allowable duration (days)	±7		±7	The visit date after randomization visit is determined in relation to the date of the randomization visit (± the allowed visit window).
Fasting visit	X	X	X	If the participant is not fasting, the participant should be called in for a new visit within the visit window.
Waist circumference	X	X	X	
Electrocardiogram		X	X	Single ECGs should be collected centrally at ED and Visit 801
Vital signs (sitting BP and PR)		X	X	Vital sign measurements should be taken before collection of blood samples for laboratory testing, at visits where required. The participant should sit quietly for 5 minutes before vital sign measurements are taken. For each parameter, 2 measurements will be taken using the same arm; the recordings should be taken at least 1 minute apart.
Clinical laboratory tests				
Hematology		X	X	
Clinical chemistry		X	X	
Other chemistry				
Cystatin-c		X	X	

Activity	Early Discontinuation and Follow-Up Period		Comment	
Visit Number	99	ED	801	At ED visit, participants who are unable or unwilling to continue the study treatment for any reason will perform an ED visit. If the participant is discontinuing during an unscheduled visit or a scheduled visit, that visit should be performed as the ED visit. At Visit 801, for participants who discontinue or complete the study within 72 weeks, Visit 801 (safety follow-up visit) should be performed 4 weeks after the last visit during the 72-week treatment period.

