4.1. Overall Design

Study GPHZ is a Phase 3, multicenter, randomized, placebo-controlled, double-blinded study to evaluate the safety and efficacy of subcutaneously administered tirzepatide 10 mg and/or 15 mg QW compared with placebo when used in conjunction with a reduced calorie diet and increased physical activity for weight management, in obesity disease participants with BMI \geq 27 and <35 kg/m² and at least 2 obesity-related health problems or BMI \geq 35 kg/m² and at least 1 obesity-related health problems. The obesity-related health problems are IGT, hyperlipidemia, or NAFLD.

The study population will be enriched for participants who have NAFLD and IGT, such that more than 40% of the total study population will consist of participants with NAFLD, and more than 60% of the total study population will consist of participants with IGT.

Study GPHZ will consist of 3 periods: a 4-week screening period, followed by a 72-week treatment period including a 20-week dose escalation, and a 4-week safety, off-drug, follow-up period. Approximately, 261 participants will be randomized in a 1:1:1 ratio to tirzepatide 10 mg, 15 mg, or placebo.

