8.9. Immunogenicity Assessments

At the visits and times specified in the Schedule of Activities (Section 1.3), venous blood samples will be collected to determine antibody production against tirzepatide.

To interpret immunogenicity results, a venous blood sample will be collected at the same time points to determine the blood concentration of tirzepatide. All samples for immunogenicity should be taken predose when applicable and possible. The actual date and time (24-hour clock time) of each sampling will be recorded. Immunogenicity will be assessed by a validated assay designed to detect ADAs in the presence of tirzepatide at a laboratory approved by the sponsor. Antibodies may be further characterized for cross-reactive binding to endogenous counterparts, and their ability to neutralize the activity of tirzepatide or endogenous counterparts. Sample collected at Visit 801 will assess immunogenicity at washout of tirzepatide (5 half-lives post end of treatment).

Treatment-emergent ADAs are defined in Section 9.4.5.

Long-term sample retention is defined in Section 10.1.11.

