Analysis Dataset	Analysis Type	Baseline	Postbaseline
SS	1.1) Treatment-Emergent Adverse Events	The baseline period is defined as the start of screening and ends prior to the first dose in of study treatment (typically at Week 0).	Starts after the first dose of study treatment and ends at the end of the study period (including off-drug follow up visit).
SS	1.2) Treatment-Emergent Abnormal Labs a , Vital Signs, and ECGs.	Baseline will include all scheduled and unscheduled measurements during the baseline period (Visit 1 to Visit 3)	Postbaseline will be defined as above (1.1). All scheduled and unscheduled measurements will be included.
SS	1.3) Change from Last Baseline to Week xx and to Last Postbaseline for Labs a ,Vital Signs, and ECGs.	The last scheduled and unscheduled non-missing assessment recorded during the baseline period defined above (1.2).	Postbaseline will be defined as above (1.1). Only scheduled visits will be included. The early discontinuation (ED) visits are considered scheduled visits.

Table GPHZ.4.1. Baseline and Postbaseline Definitions for Safety Analysis

Abbreviations: ECGs = electrocardiogram; SS = Safety Analysis Set.

For the primary and secondary efficacy endpoint analyses, data for participants with missing values at the 72-week visit will be imputed based on the method described in Section 4.3.2. Otherwise, missing values will not be explicitly imputed except for the parameters with only 1 postbaseline measure during the analysis period per schedule of activity, where last observation carried forward (LOCF) approach will be applied to impute the endpoint when ED measure is available.

End of study participation for a participant will be the earliest of date of death, date of withdrawal from further participation in the study, or date of safety follow-up visit (Visit 801). For participants considered to be lost-to-follow-up, end of study participation will be the date of lost-to-follow-up reported by the investigator. Participant data included in the database after the last date of study participation (including safety follow-up period) will be excluded from statistical analysis.

Statistical treatment comparisons will only be performed between tirzepatide 10 mg or 15 mg, and placebo. Since the trial is not adequately powered to detect difference among tirzepatide doses, comparisons among tirzepatide doses will not be performed unless otherwise specified.

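### In the SAP's safety tables, the last-postbaseline change in labs, vital signs and ECGs is taken from the off-drug Visit 801 for everyone who attends it

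*SAP*

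**What the plan says.** Table GPHZ.4.1 in SAP Section 4.1 sets baseline and postbaseline periods for three kinds of safety analysis, all on the Safety Analysis Set. Row 1.3 covers "Change from Last Baseline to Week xx and to Last Postbaseline for Labs", vital signs and ECGs. Its postbaseline period is the one in row 1.1: "Starts after the first dose of study treatment and ends at the end of the study period (including off-drug follow up visit". The one restriction that row 1.3 adds is "Only scheduled visits will be included", and ED visits count as scheduled.

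The protocol describes the follow-up as "a 4-week safety, off-drug, follow-up period" (Section 4.1). On timing, the Schedule of Activities (Section 1.3, Table 3) states that "Visit 801 (safety follow-up visit) should be performed 4 weeks after the last visit during the 72-week treatment period", for those who complete and those who discontinue, with a window of 7 days either way. On content, it says "Single ECGs should be collected centrally at ED and Visit 801", and it marks vital signs, hematology, chemistry, HbA1c, urine tests, pancreatic enzymes, calcitonin and lipids for the same visit. Protocol Section 8.9 says what the visit represents: "Sample collected at Visit 801 will assess immunogenicity at washout of tirzepatide (5 half-lives post end of treatment".

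**The concern.** A reader of a safety table normally takes the change to last postbaseline as the final value under treatment, with early leavers included. As defined here, the value is mostly an off-drug one. If the drug raises pulse or pancreatic enzymes and the effect fades once dosing stops, the column will show arms that look more alike than they were on treatment. In a safety table that errs towards reassurance.

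Row 1.3 also partly defeats its own provision for ED visits. It admits ED values, but a participant whose last treatment-period visit was ED and who then attends Visit 801 has the ED value superseded. ECGs are the most exposed. On treatment they are scheduled only at Weeks 24 and 72, plus ED, so someone who leaves the study before Week 24 may have the ED tracing as the only on-treatment ECG after baseline.

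**Working it through.** The plan states no figure to reproduce. The check traces a definition and then asks how large the effect could be.

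**Step 1. Which value is last?**
- Row 1.3 uses the row 1.1 period, which includes the off-drug follow-up visit.
- Row 1.3 keeps scheduled visits only. Visit 801 is a numbered visit with a window in the Schedule of Activities, so it qualifies.
- Vital signs, ECG and laboratory panels are all collected at Visit 801. Visit 99 collects none of the three.
- SAP Sections 4.5.3.4 to 4.5.3.6 (vital signs, ECGs, laboratory tests) do not limit last postbaseline to the treatment period.

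So the last-postbaseline value is the Visit 801 value for everyone with a result there, and the last treatment-period or ED value for everyone else.

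**Step 2. How far off drug is Visit 801?** Five half-lives leave 2^-5 = 3.1% of drug. As a cross-check, the male contraception rule in Protocol Section 5.1 equates 5 half-lives plus 90 days with 4 months:
- 30-day months: 4 × 30 − 90 = 30 days, so a half-life of 6.0 days.
- 30.44-day months: 4 × 30.4375 − 90 = 31.75 days, so a half-life of 6.35 days.

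The 4 months are rounded, so this half-life is approximate. Drug remaining = 0.5^(days since last dose / half-life):

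| Days since last dose | Half-life 6.0 d | Half-life 6.35 d |
|---|---|---|
| 21 | 8.8% | 10.1% |
| 28 | 3.9% | 4.7% |
| 35 (last dose a week before the final treatment visit, assumed) | 1.8% | 2.2% |
| 42 | 0.8% | 1.0% |

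This agrees with the protocol's description of the visit as washout.

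**Step 3. What could that do to the column?** Let f be the share of participants whose last value is from Visit 801, and r the share of the on-drug effect still present then. The share of the on-drug difference that the column keeps is (1 − f) + f × r. Neither f nor r is in the documents, so every entry below is an assumption:

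| | r = 0 | r = 0.25 | r = 0.5 | r = 1 |
|---|---|---|---|---|
| f = 0.75 | 25% | 44% | 62.5% | 100% |
| f = 0.90 | 10% | 33% | 55% | 100% |
| f = 1.00 | 0% | 25% | 50% | 100% |

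For example, f = 0.90 and r = 0.5 give 0.10 + 0.45 = 0.55. Two cautions apply. Residual drug is not residual effect, so the 3% from Step 2 cannot stand in for r; slow measures such as HbA1c may keep much more. The formula also credits everyone who misses Visit 801 with a full on-drug effect, which is generous for those who had stopped the drug well before their last visit.

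**Step 4. Does the SAP separate the periods elsewhere?** Yes. Liver test elevations (Section 4.5.5.3.3) are reported for the treatment period and for the whole study, and antidrug antibodies for the planned treatment period and for the entire postbaseline period. Row 1.3 has no such split.

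**The case against.** The strongest reply is that nothing decisive rests on this column. Last postbaseline for these measures appears only in the row 1.3 label. The operative sections compare arms by a repeated-measures model across scheduled visits (Section 4.5) and summarise vital signs, ECGs and laboratory tests by visit. Any-time extremes are analysed as well: treatment-emergent high and low vital signs, ECG limits and QTcF increases, and banded maximum pancreatic enzymes, liver tests and calcitonin. A later washout value cannot erase an earlier extreme. Blood pressure is also modelled on the Efficacy Analysis Set, which excludes data more than 7 days after the last dose. All of this stands, and it is why the point is minor. One gap remains: Section 4.5 allows an ANCOVA fallback without saying which postbaseline value it would use.

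A second reply is that keeping follow-up data matches the Safety Analysis Set and a safety estimand that disregards adherence. That justifies collecting and reporting Visit 801. It does not require a planned washout visit to serve as the final value in a change summary.

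Three stronger readings are tempting, and the documents do not support them:
- A reader might infer that this is the only mean-change summary to include early stoppers. It is not. They contribute every visit attended to the by-visit summaries and the model, and Protocol Section 7.1 keeps those who stop the drug in the study for all planned measurements.
- A reader might infer that the whole column is off-drug. It is mixed, because those without a Visit 801 result contribute an earlier value, and the mix may differ by arm.
- A reader might take a percentage from Step 3 as the expected dilution. Both inputs are assumed.

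**Conclusion.** The point holds for one descriptive column. By the SAP's own definitions, the last-postbaseline change in labs, vital signs and ECGs is an off-drug value for every participant with a Visit 801 result, and for those who left at an ED visit it displaces the ED value. For effects that reverse off drug, the direction is towards placebo. The size cannot be derived from the documents: it depends on Visit 801 attendance and on the speed of reversal of each measure, and it is nil for an effect that persists. It does not follow that the safety analysis as a whole would miss an on-drug effect, since the by-visit, model-based and extreme-value analyses are intact. The primary endpoints are not touched. The priority is minor.

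**What to change.** In Table GPHZ.4.1 row 1.3, define last postbaseline as the last scheduled value in the treatment period (Visits 4 to 21 or ED), regardless of adherence to study drug, and report Visit 801 as a separate follow-up column. Leave rows 1.1 and 1.2 as they are, so that adverse events and abnormal values are still counted through follow-up.

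Do not borrow the Efficacy Analysis Set's cut at 7 days after the last dose. It would also drop treatment-period values from participants who stopped the drug but stayed in the study, which conflicts with the stated safety estimand.

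The cost is one line of SAP text and one more table column. No new data are needed.

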#### 4.3.2.2. Main Analytical Approach for Categorical Measures

For the percentage of participants achieving at least 5% body weight reduction from randomization over time, a logistic regression model will be used with the response variable of the percentage of participants achieving at least 5% body weight reduction at each scheduled postbaseline visit.

A logistic regression model with terms of treatment group stratification factors: baseline IGT (yes or no); baseline hyperlipidemia (based on TG; yes or no); baseline NAFLD (yes or no) and sex (female, male) as fixed effects, and baseline body weight as a covariate, will be conducted for percentage of participants achieving at least 5% body weight reduction from randomization at the 72 week visit. Missing body weight measurement at 72 week will be imputed by the predicted value from MMRM model aforementioned, then the continuous measurements will be dichotomized into status of achieving at least 5% body weight reduction (Yes or No). A logistic regression will be utilized to analyze proportion of participants with at least 5% body weight reduction at each nominal visit from randomization through 72 weeks.

With the aid of the logistic regression model, 2-sided 95% CI and odds ratio for percentage of participants achieving at least 5% body weight reduction from baseline to the 72-week visit between tirzepatide 10 mg or 15 mg QW and placebo will be derived.

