Percentage of participants who met the following criteria at 72 weeks from BL	Improvement in at 2 or 3 obesity related health problems	Efficacy analysis set - participants with 3 defined obesity-related health problems	Logistic model in Section 4.3.2.2	Exploratory
	Improvement in at 2 obesity related health problems	Efficacy analysis set - participants with 2 defined obesity-related health problems	Logistic model in Section 4.3.2.2	Exploratory
	Improvement in at 1 obesity related health problems	Efficacy analysis set - participants with 3 defined obesity-related health problems	Logistic model in Section 4.3.2.2	Exploratory

Abbreviations: ANCOVA = analysis of covariance; BL = baseline; BMI = body mass index; IGT = impaired glucose tolerance; MMRM = mixed model for repeated measures; NAFLD = non-alcoholic fatty liver disease; OGTT = oral glucose tolerance test; TG = triglycerides; TZP = tirzepatide.

Table GPHZ.4.3. Secondary and Exploratory Efficacy Measures for Body Mass

Analysis variable	Criteria/Measures	Analysis set	Analysis method	Additional Information
Change in body weight (24, 52, and 72 weeks)	Proportion of participants who achieve the following criteria from BL	Efficacy analysis set	Logistic model in Section 4.3.2.2	
	
 
≥5% body weight reduction (only at 24 and 52 weeks)
 
≥7% body weight reduction
 
≥10% body weight reduction
 
≥15% body weight reduction
 
≥20% body weight reduction
 
			
	Mean percent change from BL in  • Body weight (%) (Only at 24 and 52 weeks)	Efficacy analysis set	MMRM model in Section 4.3.2.1	
	Mean change from BL in			
	

Absolute body weight (kg)

BMI

			
EWL	EWL defined in Section 4.4.1.1	Efficacy analysis set	MMRM model in Section 4.3.2.1	
Change in VAT and SAT (72 weeks)	Mean change from BL in  VAT area (cm²)  SAT area (cm²)  VAT/SAT ratio	Efficacy analysis set	ANCOVA model in Section 4.4.2.1	
	Mean percent change from BL in  VAT area (cm²)  SAT area (cm²)  VAT/SAT ratio	Efficacy analysis set	ANCOVA model in Section 4.4.2.1	

Analysis variable	Criteria/Measures	Analysis set	Analysis method	Additional Information
	Proportion of participants who achieve VAT <100 cm 	Efficacy analysis set - participants with VAT ≥100 cm² at	Logistic model in Section 4.4.2.2	
Change in waist circumference (24, 52, and 72 weeks)	Mean change from BL in waist circumference	BL Efficacy analysis set	MMRM model in Section 4.3.2.1	

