# 5. Sample Size Determination

Approximately, 348 participants will be screened to achieve 261 randomly assigned to study intervention (approximately 87 participants per intervention group).

The sample size determination assumes that evaluation of superiority of tirzepatide 10 mg and tirzepatide 15 mg to placebo will be conducted in parallel, each at a 2-sided significance level of 0.025 using a 2-sample t-test. Additionally, a difference of at least 11% mean body weight percentage reduction from randomization at 72 weeks for tirzepatide 10 mg and/or tirzepatide 15 mg compared with placebo, a common SD of 10%, and a dropout rate of 25% are assumed for statistical power calculations. Under the assumptions above, randomizing 261 participants in a 1:1:1 ratio to tirzepatide 10 mg, tirzepatide 15 mg, and placebo provides more than 90% power to demonstrate superiority of each tirzepatide dose to placebo.

The chosen sample size and randomization ratio also provides >90% power to establish superiority of tirzepatide 10-mg and/or tirzepatide 15-mg doses to placebo in terms of proportion of participants achieving at least 5% body weight reduction at 72 weeks, conducted in parallel using a Fisher's exact test, each at a 2-sided significance level of 0.025, assuming 25% of placebo-treated participants and 90% of tirzepatide-treated participants achieve the goal and a dropout rate of 25%.

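### Weight-loss responder rates at Weeks 24 and 52 use only on-drug observed weights in a single-visit logistic model, which matches the MAR-based efficacy estimand only if missingness depends on treatment and baseline covariates alone

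*SAP*

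**What the plan says.** - **Endpoints.** SAP Table GPHZ.4.3, under "Change in body weight (24, 52, and 72 weeks", lists the proportions losing at least 5% (Weeks 24 and 52 only), 7, 10, 15 and 20% of body weight. It assigns all of them to the logistic model of Section 4.3.2.2 on the EAS.
- **Data.** For body weight, the EAS (SAP Section 3) removes everything later than 7 days after the last dose.
- **Model.** Section 4.3.2.2 says "Missing body weight measurement at 72 week will be imputed by the predicted value from MMRM model aforementioned" and then dichotomises. It goes on to fit a logistic regression at each nominal visit, with treatment, the stratification factors and baseline weight. There is no visit term and no link between a person's visits.
- **Missing values.** Section 4.1 limits imputation for primary and secondary efficacy endpoints to the 72-week visit and continues: "Otherwise, missing values will not be explicitly imputed except for the parameters with only 1 postbaseline measure". For those single-measure parameters it uses LOCF.
- **Target.** SAP 1.1.2.1 defines the efficacy estimand for all treated randomised participants, with a hypothetical strategy for stopping treatment. Protocol 9.4.3.1 attaches a missing-at-random assumption to it. The closing text of SAP 4.4.3 has secondary objectives guided by the same estimand in the same population.
- **Protocol method.** Protocol 9.4.3.1 and 9.4.3.2 plan longitudinal logistic regression for the 5% endpoint and for other categorical efficacy endpoints. SAP 4.4.2.3 contains such a model, but Table GPHZ.4.3 does not use it for weight. SAP 4.9 does not mention the change.

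**The concern.** Under MAR, the chance of stopping drug may depend on weights already recorded. A person who has lost little by Week 16 and then stops has informative weights on file, and an MMRM uses them. The single-visit logistic model discards that person at Weeks 24 and 52. If poor responders stop more often, the observed responder rate is too high, and the between-arm difference shifts by the gap between the two arms' biases.

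Two comparisons within the report are affected. Mean percent weight change at Weeks 24 and 52 comes from the MMRM, so the same scale readings at the same visit are analysed under two missing-data assumptions. Responder rates at Weeks 52 and 72 are also computed differently, so a change between them mixes method with effect.

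**Working it through.** **1. The plan's own figure.** SAP Section 5 supplies the inputs: "randomizing 261 participants in a 1:1:1 ratio to tirzepatide 10 mg, tirzepatide 15 mg, and placebo"; "a difference of at least 11% mean body weight percentage reduction from randomization at 72 weeks"; "a common SD of 10%, and a dropout rate of 25% are assumed for statistical power calculations"; and testing "each at a 2-sided significance level of 0.025 using a 2-sample t-test".
- Evaluable per arm: 87 × 0.75 = 65.
- Noncentrality: 11 / (10 × √(2/65)) = 11 / 1.754 = 6.27, giving power of about 99.99%.
- Fisher's exact test for 25% against 90% with 65 per arm gives more than 99.99%.

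The claim of more than 90% power is met. The point here concerns secondary estimates, not power.

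**2. Does the LOCF exception cover weight?** No. The Schedule of Activities has postbaseline weights at Weeks 4, 8, 12, 16, 20, 24, 36, 48, 52, 60 and 72, which is 11 measurements.

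**3. How many drop out of the analysis?** Only the 25% total is stated, so its timing is an assumption.
- Linear accrual, Week 24: 25% × 24/72 = 8.3%, leaving about 80 of 87 per arm.
- Linear accrual, Week 52: 25% × 52/72 = 18.1%, leaving about 71.
- All dropout early: about 65 at both visits.

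**4. Size of the bias.** This is a simulation of 400,000 per arm. It assumes Week 72 means of -2% and -13%, SD 10%, and 21-25% off drug by Week 72. The dropout hazard rises by a factor of 1.6 or 2.7 per SD less weight loss at the last observed visit. Entries are the observed-case rate minus the true rate for at least 5% loss, in percentage points.

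| Dropout hazard, factor per SD | Wk 24 placebo | Wk 24 active | Difference | Wk 52 placebo | Wk 52 active | Difference |
|---|---|---|---|---|---|---|
| constant, 1.6 | +1.1 | +1.4 | +0.3 | +2.6 | +2.5 | -0.1 |
| constant, 2.7 | +1.6 | +2.6 | +1.0 | +4.1 | +4.6 | +0.5 |
| front-loaded, 1.6 | +2.7 | +3.5 | +0.8 | +2.9 | +2.7 | -0.2 |
| front-loaded, 2.7 | +4.0 | +6.0 | +2.0 | +4.6 | +4.8 | +0.2 |

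- Dropout unrelated to weight: bias of 0.1 points or less.
- Same mechanism in both arms: difference biased by -0.2 to +2.0.
- Weight-dependent in placebo only: -1.1 to -4.0 (Week 24) and -2.6 to -4.6 (Week 52).
- Weight-dependent in tirzepatide only, from the same columns: +1.4 to +6.0 (Week 24) and +2.5 to +4.8 (Week 52).

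A second set of assumptions has 20% missing by Week 52, dropout odds changing 1.6- to 2.2-fold per SD, and a true placebo rate of 25%. The placebo rate then becomes 27-29%. The difference is biased by -4 to +2 points for 5% loss and -2 to +3 for 10% loss, depending on which arm loses its non-responders.

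**5. Week 52 against Week 72.** In the first simulation (placebo, constant hazard, factor 1.6) the true 5% responder rate rises from 36.5% to 38.2%, or +1.7. The SAP would report 39.1% observed at Week 52 and 36.1% by predicted value at Week 72, or -3.0.

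**6. Would extending the Week 72 method cure it?** No. A single predicted value at Week 52, in the table's four scenarios in order, biases placebo by -1.4, -1.3, -2.7 and -2.2, and active by +0.9, +0.3, +1.8 and +0.9. Active minus placebo gives +2.3, +1.6, +4.5 and +3.1. With the same mechanism in both arms, that is worse than leaving the values missing.

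**The case against.** - **The text may intend imputation at every visit.** Section 4.3.2.2 describes impute-then-dichotomise and then moves to each nominal visit. That is a possible intent, but Section 4.1 says otherwise. If it was intended, the SAP must state it, and step 6 shows it would not be enough.
- **No Week 24 or 52 estimand is written out.** True: SAP 1.1.2.1 is worded for Week 72, and secondary objectives are only guided by it. But the documents name no other target for these visits.
- **Missing imputation is not a fault in itself.** This stands. A likelihood-based longitudinal model would use the earlier weights without imputing. The problem is no imputation combined with a single-visit model.
- **The magnitude is assumed.** This stands too. No document gives a dropout mechanism. The first simulation's normal model implies Week 72 rates of 38.2% and 78.8%, not the planned 25% and 90%. Both simulations compare raw proportions, whereas the SAP reports adjusted odds ratios.
- **The bias is small beside the noise and the effect.** With 71 per arm, the standard error of a 25% against 90% difference is √(0.25×0.75/71 + 0.90×0.10/71) = 0.063, or about 6 points, and the planned Week 72 difference is 65 points. This limits the consequence but does not make the two analyses consistent.

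A reader might infer that these are analyses of study completers. They are not: someone who stops drug at Week 40 still counts at Week 24. The group is those with an on-drug weight at that visit.

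**Conclusion.** The inconsistency is real and of moderate importance. At Weeks 24 and 52 the responder analyses rest on a stronger assumption than the MAR assumption the protocol states: that missingness depends on treatment and baseline covariates alone. They disagree in method with the MMRM at the same visits, with the Week 72 analysis and with the protocol's longitudinal model, and SAP 4.9 is silent on the change.

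The bias in the 5% responder difference is about zero if dropout is unrelated to earlier weight. It runs from about -4.6 to +2 points when dependence is confined to placebo or shared by all arms. If dependence were confined to the tirzepatide arms, the same simulation gives up to +6.0. The sign is not predictable in advance.

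Two stronger inferences are not supported. One is that these results necessarily miss the estimand; they do so only if discontinuation depends on earlier weight change. The other is that the trial's conclusions are at risk. Only the two Week 72 hypotheses are alpha-controlled (SAP 2.1), and the planned effect is far larger than the bias.

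**What to change.** Amend SAP 4.1 and 4.3.2.2 so that missing on-treatment body weights at Weeks 24 and 52 are multiply imputed under one MAR model containing treatment, stratification factors, baseline weight and intermediate weights. Dichotomise at each threshold, fit the visit-wise logistic models, and pool by Rubin's rules, which SAP 4.3.3.1 already uses for the supplementary ANCOVA. Use the same imputed set at Week 72, so that all three visits share one method. List the departure from the protocol's longitudinal logistic regression in SAP 4.9.

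Pointing Table GPHZ.4.3 to the model in SAP 4.4.2.3 is a weaker alternative: that section names no estimation method, so validity under MAR is not assured.

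The cost is SAP wording and modest extra programming, with no new data. The Week 72 co-primary responder analysis would change as well, so the amendment should be settled before unblinding.
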